3.2.1 Appropriateness of Measurements

The efficacy endpoints chosen for the study are based on those that have been commonly used during routine clinical practice in adults (Logigian *et al.*, 2010; Statland *et al.*, 2012a; Statland *et al.*, 2012b), but they have been adapted according to the patient's age and ability to participate in the efficacy evaluation. The Sponsor has also received feedback from KOLs regarding what measures are considered appropriate for different ages. Moreover, the approach to and the scope of efficacy endpoints was accepted by the Regulatory Authorities (in particular the Paediatric Committee; PDCO) during the evaluation and discussion on the paediatric investigation plan (PIP) that this protocol is specifically designed to support.

Similarly, the safety parameters proposed are also in line with the conventional endpoints to evaluate safety and are suitable for use in the paediatric population.

3.2.2 Control Group

Not applicable as it is a single arm, non-comparative study.

3.2.3 Duration of Study

The overall treatment duration follow-up for each patient will be 2 years.

3.3 Selection of Study Population

3.3.1 Inclusion Criteria

- 1. Male or female patients from birth to less than 6 years
- 2. A genetically confirmed diagnosis of NDM or DM (DM1or DM2), as per the treating clinician.
- 3. Presence of clinical symptoms of myotonia (hand grip myotonia, myotonia in the leg muscles, any other myotonia symptoms) to be confirmed by the treating clinician.
- 4. Patients already receiving mexiletine treatment or who are clinically considered for mexiletine treatment as per the treating physician judgement.
- 5. No history of or significant cardiac abnormalities as determined by a cardiologist's assessment of the ECG and echocardiogram performed prior to enrolment in the study or as per the treating physician standard of care (NaMuscla SmPC, 2023)
- 6. No known history or signs and symptoms of any significant liver disorder as per treating physician.
- 7. No known clinically relevant abnormal laboratory investigations for haematology, biochemistry, and urinalysis values at screening (or based on values obtained within 3 months prior to screening in patient's medical record) that could affect the study objectives as judged by the treating physician.
- 8. Parent or legal guardian able to provide assent to study participation and to sign the written informed consent prior to study entry and perform any study-related activity.

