3.2 Discussion of Study Design

Study inclusion screening time will be approximately 2 weeks.

Patients who meet the eligibility criteria will be enrolled in two cohorts by age groups although cohorts are not planned to necessarily enrol sequentially (cohort definition is to assure minimum requirements for meeting PIP agreements).

- Cohort 1 Infants and children aged between 6 months to less than 6 years.
- Cohort 2 Neonates and infants from birth to less than 6 months.

The overall treatment duration follow-up for each cohort will be at least 2 years.

Dosing and treatment administration in this registry study should be done as per the treating physician clinical practice.

Visits to the clinic are to occur according to routine site's clinical practice, or when applicable according to the treating practice physician.

An initial visit (i.e., screening equivalent that will also serve as baseline) will take place to ensure the patient currently complies with all participation. This visit will serve for the patient to enter the study.

The end of treatment (EOT) visit will be the first routine clinical practice visit after at least 2 years have been completed since the patient entered the study (baseline visit) or 2 weeks after the last mexiletine intake after 2 years of treatment (whichever occurs first).

After 24 months, no study specific visits and data collection are required and patients will be treated and followed up as per the investigator's site protocol.

The following data elements will be collected during this registry, as permitted by the clinical site normal clinical practice for patients with myotonic disorders and according to the patient's age, using as the example other myotonia registries (Lagrue *et al.*, 2019).

- Demographics
- Genetics: DM1, DM2 or NDM corresponding clinical forms
- Musculoskeletal manifestations (myotonia, facial hypotonia)
- Orthopaedic deformities (spine, feet or hands, orthoses, back brace, specialized followup, surgery)
- Cardiorespiratory signs (non-invasive ventilation, sleep disorders, ECG / left ventricular ejection fraction (LVEF), pacemaker/defibrillator)
- Ophthalmic and endocrinologic manifestations (cataract, diabetes, thyroid disorders)
- Psychomotor development disabilities
- Gastrointestinal (GI) disorders
- Patterns of mexiletine use including dose/ frequency.

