Data will be entered at baseline upon patient enrolment and entered periodically thereafter for all routine clinical practice patient visits. For example, all laboratory values collected at routine clinical visits occurring between month 6 and month 12 of a patient's participation in the registry should be entered at the 12-month time point. All data will include the date each assessment was performed. Where available, additional retrospective data will be collected. Retrospective data will be focussed primarily on patterns of mexiletine use and dose adjustments as well as any efficacy assessments. Retrospective safety data will also be recorded, especially in relation to any AEs that affect dosing, SAEs or AESIs, but there will be no requirement to report any retrospective AEs prior to signing the informed consent. In cases where retrospective data are captured, this will be recorded from first mexiletine prescription up to the baseline visit or to the maximum age of eligibility for entering into the trial (that is, up to 6 years). For eligible patients who provide informed consent, data elements will be extracted from the information routinely recorded in the medical records and transcribed in to the electronic Case Report Forms (eCRF). Safety, treatment administration and efficacy assessments will be collected during the visits. AEs will be collected from the time informed consent is given to end of treatment.

No drug safety monitoring committee (DSMB) will be created.

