8.1.1 Adverse Event

An AE is defined as any untoward medical occurrence in a patient or clinical investigation patient administered a pharmaceutical product and which does not necessarily have a causal relationship with this treatment. An AE can, therefore, be any unfavourable and unintended sign, symptom or disease (including intercurrent illness), deterioration of a pre-existing illness, accident, any suspected drug reaction, or a clinically relevant change of laboratory values temporally associated with the use of a medicinal (investigation) product, whether or not related to the medicinal (investigational) product and/ or study treatment.

A treatment emergent AE (TEAE) will be defined as an AE that begins or that worsens in severity after at least one dose of study drug has been administered.

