8.14 Safety Analysis

All summaries of adverse events will use only treatment emergent adverse event (TEAE) records.

In general, events will be described by counts and percentages.

Following information will be summarized for TEAEs.

- Overall Summary of TEAEs
- TEAEs by preferred term and System Organ Class (SOC)
- Treatment Related TEAEs by preferred term and SOC
- TEAEs by preferred term and SOC, Maximum Severity and Relationship
- Serious TEAEs by preferred term and SOC

• TEAEs leading to discontinuation of study drug by preferred term and SOC

Also, listing of all adverse events will be provided. The listing will include Adverse event number, description, preferred term, SOC, Start and End Date, Seriousness, Frequency of Occurrence, Severity, Action taken regarding study treatment, outcome, relationship to study treatment.

When collected laboratory and vital signs parameters will be summarised descriptively. Laboratory tests done at screening will be considered baseline.

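### Children already on mexiletine get an on-treatment baseline, so the Section 8.13 changes from baseline mix two quantities; the treatment-emergent definition also has no consent bound

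*Protocol*

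**What the plan says.** **Who enters.** Protocol Section 3.3.1, criterion 4, admits "Patients already receiving mexiletine treatment or who are clinically considered for mexiletine treatment as per the treating physician judgement". New starters and continuing users are both eligible, and no share or cap is given for either.

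**Baseline.** Section 3.2: "An initial visit (i.e., screening equivalent that will also serve as baseline) will take place". This holds whatever the prior exposure. Section 5.1 mandates no mexiletine washout.

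**Retrospective data.** Section 3.2: "Where available, additional retrospective data will be collected". Of the window it says "this will be recorded from first mexiletine prescription up to the baseline visit", or up to the age limit for entry. The content is mainly use and dose changes, plus any efficacy assessments. Retrospective safety data are to be recorded too, but reporting of events before consent is not required.

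**Efficacy summaries.** Section 8.13 lists change from baseline for Faces, hand relaxation time, TUG, quality of life, CGI and MBS. The synopsis states presentation for all patients and by age cohort. Section 3.2.2 confirms that there is no control group.

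**Adverse events.** Section 8.1.1 defines a treatment-emergent event as "an AE that begins or that worsens in severity after at least one dose of study drug has been administered". Section 8.14: "All summaries of adverse events will use only treatment emergent adverse event (TEAE) records". Section 8.1.3 starts AE reporting at informed consent.

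**The concern.** With no control group, change from baseline is the main efficacy contrast within a child. In a new starter it spans the start of treatment. In a continuing user it shows maintenance, dose adjustment, growth and disease course while on drug. A mean over both groups estimates neither quantity, and its value depends on how many of the roughly ten children were already treated at entry.

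The time origin for safety has a related gap. Mexiletine is obtained by ordinary prescription, so nothing in the treatment-emergent definition separates a first-ever dose from a first dose after consent. A continuing user's pre-consent event can meet the definition. Such events enter the database only when someone chose to record them, so an event count could combine systematic and selective collection.

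Efficacy is exploratory, but it sits in the primary objective (Section 2.1.1) and feeds the risk-benefit text in Section 6.2.

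**Working it through.** **Plan's own figure.** Section 8.8 asks for at least 4 children in cohort 2 and at least 6 in cohort 1: 4 + 6 = 10, which agrees with the stated total. Section 1.3 states that there is no hypothesis testing, so there is no power calculation to reproduce.

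**What the baseline visit measures.**

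| | New starter | Continuing user |
|---|---|---|
| Enrolment visit | before drug | on drug |
| Change from enrolment | pre-treatment to on-treatment | on-treatment course |
| Assessment before first prescription | not needed | outside the window |
| Assessment at the prescribing visit | not needed | may be captured, not designated as baseline |

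**Illustration of size.** Let D be the true mean change from pre-treatment to on-treatment, taken as equal in both groups. Let f be the share already on mexiletine at enrolment, and r the fraction of D that still occurs after enrolment in those children. Then

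pooled mean change / D = (1 − f) + f × r.

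The protocol gives neither f nor r; both are assumptions. With 10 children:

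| Already treated | r = 0 | r = 0.25 |
|---|---|---|
| 0 | 100% | 100% |
| 2 | 80% | 85% |
| 4 | 60% | 70% |
| 6 | 40% | 55% |
| 8 | 20% | 40% |
| 10 | 0% | 25% |

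For example, with 4 treated and r = 0.25: 0.6 + 0.4 × 0.25 = 0.70. At r = 1 there is no distortion whatever f is; for any r below 1 the pooled figure is too small. Values of r below 1 are the likelier case, because part of the response precedes enrolment.

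Two features of the protocol keep r uncertain. Criterion 3 requires clinical symptoms of myotonia, so continuing users may be partial responders with room to change. Two years of growth also shifts timed and functional measures in both groups, which the formula leaves out.

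**Safety wording side by side.** Section 8.1.1 sets one condition: onset or worsening after a dose. Section 8.1.3 starts collection at consent. Section 3.2 lets earlier events be recorded without requiring it. Section 8.12 requires a dose after consent for the Safety Population, but that selects children, not events. No sentence removes a recorded pre-consent event in a continuing user from the Section 8.14 tables.

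**The case against.** The strongest reply is that this is a descriptive, non-interventional registry whose secondary aim is to learn how mexiletine is used. Enrolling current users belongs to that design, and a separate SAP can split tables by prior exposure. Screening item 16 (Section 5.1) records prior mexiletine dosing, so the case mix can be reported. This lowers the severity. It does not answer the point about data: the protocol itself fixes the baseline visit and the retrospective window, and an SAP cannot recover assessments that were never collected.

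Several stronger readings are tempting and are not supported:

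- *Change from baseline says nothing about treatment.* New starters have a pre-dose baseline, although their change is uncontrolled.
- *Every efficacy measure is affected.* Section 8.13 does not list MRC strength, FLACC or PIPP. Observed CGI values rate efficacy directly and need no baseline.
- *No untreated value can ever be captured.* An assessment at the prescribing visit can fall inside the window.
- *Most children will be continuing users, because Section 2.1.2 refers to clinicians who had already chosen mexiletine.* Section 1.4 says that the prescribing decision precedes inclusion for all patients, so the phrase covers new starters too. With 4 and 6 children per cohort, 8 of 10 already treated would need at least 8 − 6 = 2 infants under 6 months on drug at entry.
- *Reactions that began on mexiletine before consent are discarded as pre-existing.* Section 8.1.3 speaks of diseases, while Section 3.2 provides for recording retrospective safety data. The reading is contestable.
- *Pooled AE percentages understate early harm by a known amount.* Continuing users are past their first exposure at consent, so the tables mix early and later exposure, but the documents give no basis for a size.

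**Conclusion.** The point holds for continuing users and for any summary that pools them with new starters. As written, the Section 8.13 changes from baseline combine on-treatment course with change across treatment start. The direction is probably towards understating change. The size is unknown: the percentages in the working rest on an assumed share of continuing users, an assumed residual change and an equal true effect in both groups, and should not be quoted as estimates.

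The safety part is narrower: the treatment-emergent definition permits selectively recorded pre-consent events to be counted; it does not require it.

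Severity is should-fix. Efficacy is exploratory and descriptive, but the repair is cheap and changes what the tables can support.

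**What to change.** 1. Record the date of first mexiletine dose. Present the Section 8.13 efficacy summaries and the AE tables separately for new starters and continuing users.
2. Extend retrospective capture back to the last available assessment before the first dose. Use it as the pre-treatment baseline where it exists and suits the child's age. Otherwise label the continuing users' result *change since enrolment (on treatment)*.
3. Restrict treatment-emergent tables to events with onset or worsening on or after consent and after a dose. List retrospective events separately.

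**Cost.** Revised protocol wording, an eCRF page for the pre-dose assessment and first-dose date, and some extra tables; no added visits. The subgroups will be small at about 10 children, and fewer will have a true pre-treatment change. The loss is greatest for TUG, which the protocol limits to age 3 years and over, and for Faces, which it describes for children aged 6 years: a child first treated earlier in life cannot have an age-appropriate pre-dose value.

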3.3.2 Exclusion Criteria

- 1. Any contraindication to mexiletine as listed in the Namuscla Summary of Product Characteristics (SmPC) (NaMuscla SmPC, 2023)
 - a) Hypersensitivity to the active substance, or to any of the excipients
 - b) Hypersensitivity to any local anaesthetic
 - c) Ventricular tachyarrhythmia
 - d) Complete heart block (i.e., third-degree atrioventricular block) or any heart block susceptible to evolve to complete heart block (first-degree atrioventricular block with markedly prolonged PR interval (≥ 200 ms) and/or wide QRS complex (≥ 120 ms), second-degree atrioventricular block, bundle branch block, bifascicular and trifascicular block),
 - e) QT interval > 450ms
 - f) Myocardial infarction (acute or past), or abnormal Q-waves
 - g) Symptomatic coronary artery disease

- h) Heart failure with ejection fraction <50%
- i) Atrial tachyarrhythmia, fibrillation or flutter
- j) Sinus node dysfunction (including sinus rate < 50 bpm)
- k) Co-administration with medicinal products inducing torsades de pointes.
- 1) Co-administration with medicinal products with narrow therapeutic index
- 2. Any other neurological or psychiatric condition that might affect the study assessments, as per the treating clinician.
- 3. Any clinically significant illness, laboratory findings, ECG, or other clinical symptoms, which in the opinion of the treating physician could affect the patient's optimal participation in the study
- 4. Receiving strong inducers or inhibitors of CYP2D6 or CYP1A2 or planned to receive them, during the subject participation (See section 4.1.5.1 Prohibited medications)
- 5. Any concurrent illness, or medications which could affect the muscle function, and confound the results according to the treating physician.
- 6. Seizure disorder, diabetes mellitus requiring treatment by insulin.

3.3.3 Withdrawal of Patients

In accordance with the Declaration of Helsinki and the informed consent form, patients may discontinue the study at any time without any penalty or loss of benefits to which the patient is otherwise entitled. For all patients withdrawn from the study, efforts will be made to ascertain the reason for withdrawal.

A withdrawn patient is one who meets any of the following withdrawal criteria stated below and whose study participation is discontinued. The reasons for patient withdrawal will be recorded in the case report form, signed, and dated at the last assessment visit.

Criteria for Withdrawal from Study

A patient may be withdrawn from the study due to any of the following withdrawal criteria:

- A patient's desire/ or guardian decision to withdraw for any reason (withdraws consent)
- Lost to follow-up (every effort must be made to contact the patient; the effort to contact must be documented in the Investigator's file)
- Inability of patient to comply with the Protocol for any reason
- The patient needs emergency treatment or is unable to continue participation in the trial due to the exacerbation of symptoms.
- If in the Investigator's opinion that continuing the patient in the trial is not appropriate, the Investigator may withdraw a patient at any time if it is considered to be in the patient's best interest.
- Withdrawn patients will be replaced to comply with the agreed minimum number of patients with PDCO.

Criteria for Treatment Discontinuation

• An adverse event, which in the opinion of the Investigator and/or Sponsor, necessitates discontinuation of treatment.

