The number of patients in this study is not hypothesis driven; rather as agreed with PDCO, in that at least 10 evaluable subjects will be sufficient to assess efficacy and safety of mexiletine in this ultra-rare paediatric subpopulation for the age group of 0- 6 years old.

Statistical Analysis:

Summary descriptive statistics will be provided for all collected parameters. The categorical variables will be presented with frequency and percentages.

The analysis will be performed for all patients as well as by age cohort.

Overall data collected will be analysed to assess the safety and acceptability/palatability of different modes of mexiletine administration (i.e., capsule, sprinkled on food and/or gastric (enteral) tube where such formulations are used), and the factors that govern the route of administrations in paediatric patients.

If performed and available -as per the normal disease management of each participating site, and age-appropriate- the following will be analysed and presented:

- Change from baseline in time (in seconds) to relaxation of hand muscles and reduction in relaxation time from the first to the third/fifth contraction and time (in seconds) for Timed-up and go (TUG) test will be summarized.
- The actual Faces scores and the change from baseline in Faces score for muscle stiffness, pain, weakness and fatigue will be summarized.
- Quality of life data will be presented descriptively along with the change from baseline.
- The observed values of Clinical Global Impression (CGI) Scores and the change from baseline in CGI Scores assessed by the caregivers and investigators.
- The observed values of Myotonia Behaviour Scale (MBS) Scores and the change from baseline in MBS from baseline will be summarized.

The detailed statistical treatment of the data and any analysis methods will be specified in a

Statistical Analysis Plan (SAP)

TABLE OF CONTENTS

OR SIG	NATUR	E PAGE	2
SYNO	PSIS		
OF CO	NTENTS	S	
F TABL	.ES		
F FIGU	RES		
INTRO	DUCTIC)N	
1.1	Backgro	bund to myotonic disorders	
	1.1.1	Myotonic dystrophies type 1 and 2 (DM1 and DM2)	17
	1.1.2	Non-dystrophic myotonic disorders (NDM)	
	-		
2.1	Study O		
	2.1.1	The Primary objectives	25
	2.1.2	Secondary objectives	25
STUDY	DESIG	N	
3.1	Overall	Study Design	
3.2	Discussi	ion of Study Design	
	3.2.1	Appropriateness of Measurements	27
	3.2.2	Control Group	
	3.2.3	Duration of Study	
3.3	Selectio	n of Study Population	
	3.3.1	Inclusion Criteria	
	3.3.2	Exclusion Criteria	

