Congenital DM1 shows a distinct clinical phenotype with distinct clinical features. These patients present at birth with marked generalised hypotonia and hyporeflexia and difficulties breathing and feeding which cause respiratory distress that needs assisted ventilation. Mortality in congenital DM1 during the neonatal period has been estimated at between 30% and 40% of patients. Some children who survive may die later from sudden infant death syndrome, or from respiratory failure (Hageman *et al.*, 1993). In severely affected patients surviving the neonatal period, as in less severely affected patients, the disease course is very much the same: the most constant feature is mental delay, preceded by speech and language delay, that exists in all cases and progressively worsens after several years of evolution. In these forms, signs of central nervous system dysfunction predominate, with mental deficiency and/or psychiatric disturbances. Motor development is delayed in most cases, the children becoming ambulant after the age of 2 years. But in terms of muscular weakness and the development of myotonic syndrome, disease progression is markedly variable from one patient to another (Echenne and Bassez, 2013).

DM2 is not normally diagnosed until adulthood with symptoms beginning in the second to sixth decade (median age 48 years) with variable manifestations including early-onset cataracts (younger than 50 years), varying grip myotonia, thigh muscle stiffness, and muscle pain, as well as weakness (Meola and Cardani, 2015b). Overall, it is considered that myotonia is less apparent in DM2 compared with DM1, being difficult to elicit by standard electromyography (EMG) testing except for proximal muscles such as the tensor fascia lata and vastus laterali. In cases of late-onset DM2, myotonia may only appear by EMG testing after examination of several muscles. In general, patients with myotonic dystrophy type 2 have clinical symptoms that are usually milder (Turner and Hilton-Jones, 2010).

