1.4 Regulatory background

On 7 July 2016 an application for a paediatric investigation plan (PIP) and deferral was submitted by the applicant Lupin (Europe) Ltd. And on 2 June 2017 the EMA granted a positive decision (P/0155/2017).

The applicant submitted on 26 June 2017 a Marketing Authorisation Application (MAA) for Namuscla through the centralised procedure. Subsequently, the PDCO was requested by the Agency to initiate a partial compliance procedure (EMEA-C1-002012-PIP01-16) which started on 18 July 2017 with a positive outcome on 15 August 2017.

On 18 October 2018, the Committee for Medicinal Products for Human Use (CHMP) adopted a positive opinion, recommending the granting of a marketing authorisation for the medicinal product Namuscla, intended for the treatment of myotonia in adults with certain hereditary muscle disorders (EMA/CHMP/650838/2018). The date of issue of the marketing authorisation valid throughout the European Union was 18th December 2018.

Several modifications to the initial PIP have been submitted and agreed and the current decision is P/0300/2023 for EMEA-002012-PIP01-16-M04. An additional modification (M05) was submitted in February 2024 and is ongoing. The changes in former modification M03 introduced the requirement for the current registry study, referred to as a prospective, long-term observational study (registry) of paediatric myotonic disorder patients from birth to less than 6 years of age who are treated with mexiletine. The study population was to include patients with myotonic disorders (DM1, DM2, and NDM) with a total of at least 10 paediatric subjects evaluable for the primary analysis with at least 4 patients in the birth to less than 6 in the in the 6 months to less than 6 years. Each participant must be followed for at least 2 years.

Based on epidemiological data, approximately 2 in 10,000 people are affected with myotonic disorders (which comprise the two main entities, myotonic dystrophies and non-dystrophic myotonias) in the EU. Consequently, mexiletine was granted orphan designation for "treatment of myotonic disorders" EU/3/14/1353 (EMA/OD/074/14). Namuscla was subsequently designated as an approved orphan medicinal product in the indication treatment of myotonic disorders after granting of the CHMP positive opinion. No protocol assistance procedure has ever been performed.

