4.1.4 Patient Compliance

Compliance will be assessed by drug intake history. The number of capsules or amount of powder (and way it is subsequently administered, such as yoghurt, juice etc.) as well as the dose (strength) of study drug taken daily and weekly will be captured and this data will be later transcribed into the CRF.

Patients/caregivers judged to be non-compliant will be counselled on the importance of daily intake of study medication, as prescribed. A compliance between 80% - 125% will be desired for the adequate assessment of the study outcomes. Patients who are repeatedly non-compliant or have a compliance of less than outside 80-125% may be discontinued, at investigator's discretion after discussion with the medical monitor. Replacement of subjects will be at sponsor's discretion.

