8.12 Analysis Population

Safety Population: Safety population will comprise of the subjects who received at least one dose of mexiletine after the ICF was signed by their parents or legal guardians.

Intent to Treat (ITT) Population: ITT population will comprise of the subjects who have taken at least one dose of the study treatment and have at least one post-enrolment assessment done.

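### Children may be withdrawn from the registry, and replaced, because of outcomes it is meant to record; this can bias later efficacy summaries and miss late adverse events, and the replacement rules conflict

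*Protocol*

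**What the plan says.** - **Leaving the study.** Protocol section 3.3.3 has two lists. The one for stopping treatment contains only an adverse event. The one for withdrawal from the study includes inability to comply with the protocol and "The patient needs emergency treatment or is unable to continue participation in the trial due to the exacerbation of symptoms". Withdrawal is permitted, not required.
- **Replacement.** The same section states that "Withdrawn patients will be replaced to comply with the agreed minimum number of patients with PDCO". Section 4.1.4 says that "Patients who are repeatedly non-compliant or have a compliance of less than outside 80-125% may be discontinued", at the investigator's discretion after discussion with the medical monitor, and there leaves replacement to the sponsor. It does not say whether the child is discontinued from mexiletine or from the study.
- **Analysis sets.** Section 8.12 limits the ITT population to "subjects who have taken at least one dose of the study treatment and have at least one post-enrolment assessment done". The Safety population needs only one dose after consent. Section 8.10 does not impute missing values.
- **Follow-up.** Section 1.4 reports the PIP requirement as "Each participant must be followed for at least 2 years".
- **Numbers.** Section 8.8 asks for at least 10 evaluable children, 4 in cohort 2 and 6 in cohort 1. The synopsis states that "The number of patients in this study is not hypothesis driven". The term evaluable is not defined.

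**The concern.** The registry mandates no treatment and takes its data from routine records (sections 3.1, 3.2 and 4.1.1). Its purpose is to learn how children fare on mexiletine and how it is used. Worsening bears on efficacy, and emergency care on safety. Treatment interruptions are a primary variable (section 6.1), and compliance, acceptability and palatability are listed outcomes in the synopsis. A rule that lets these events end participation makes the loss of data depend on the outcome.

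Mexiletine is prescribed through the ordinary route (section 4.2.2), so leaving the registry need not mean stopping the drug. A withdrawn child could still be exposed while new adverse events go unrecorded. The analysis plan cannot recover data that were never collected, so this has to be settled in the protocol.

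**Working it through.** **Figure in the plan.** The cohort minima agree with the total: 4 + 6 = 10. This number was agreed with the paediatric committee. There is no power or precision calculation and no dropout allowance to reproduce.

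**Passages side by side.**

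1. Section 3.3.3 makes replacement of withdrawn children a rule; section 4.1.4 makes replacement a choice. A child who leaves for non-compliance can fall under both, so they contradict each other.
2. Section 1.4 places the two-year requirement on each participant. Replacement protects the count of 10 but does not give the withdrawn child two years of follow-up.
3. Section 8.12 requires a post-enrolment assessment for the ITT set. Section 5 expects routine visits at most 6 months apart, so a child who leaves before the first one drops out of that set. Section 8.13 does not name the set used for efficacy; I assume it is the ITT set.
4. A child with one later assessment stays in the ITT set but has no values after leaving. Without imputation, the Week 104 summaries rest on children who stayed.

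**Illustration of size.** The withdrawal share and the outcomes of withdrawn children are assumptions, because the protocol gives neither.

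*Enrolment implied by replacement*, with withdrawal share w, is 6/(1 − w) plus 4/(1 − w), each rounded up:

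| Assumed w | Cohort 1 | Cohort 2 | Total enrolled |
|---|---|---|---|
| 10% | 6.67 → 7 | 4.44 → 5 | 12 |
| 20% | 7.50 → 8 | 5.00 → 5 | 13 |
| 30% | 8.57 → 9 | 5.71 → 6 | 15 |
| 40% | 10.00 → 10 | 6.67 → 7 | 17 |

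*Response share.* Suppose 6 of 10 retained children respond, and k children were withdrawn and replaced without responding. The share is 6/10 among those retained and 6/(10 + k) among all enrolled:

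| k | Retained | All enrolled |
|---|---|---|
| 1 | 60% | 6/11 = 55% |
| 2 | 60% | 6/12 = 50% |
| 3 | 60% | 6/13 = 46% |
| 4 | 60% | 6/14 = 43% |

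The retained figure is the higher one whenever the children who leave did worse than those who stay. How much higher depends wholly on the assumptions.

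**The case against.** The protocol has several safeguards:

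- Withdrawal is optional.
- Every child dosed after consent stays in the Safety population.
- Existing adverse events are followed until they resolve or stabilise, as far as feasible (sections 8.1.3 and 8.1.4.3).
- End-of-treatment assessments are to be attempted after permanent discontinuation of the medication (section 4.1.1.2).
- Discontinuations are tabulated with reasons and listed by child (section 8.11). With about 10 children, each exit would be visible.
- Efficacy is exploratory, and not imputing is acceptable in a descriptive study.

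All of this stands, and it narrows the point. It does not restore efficacy values after withdrawal or capture adverse events that begin later. The end-of-treatment attempt is tied to stopping the drug, and a single assessment is not two years of follow-up.

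Three stronger readings are tempting, but the documents do not support them.

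- A reader might infer that "After 24 months, no study specific visits and data collection are required" breaks the PIP commitment. But 24 months is two years, and the sentence directly follows the definition of the end-of-treatment visit. At most the wording is loose.
- A reader might infer from "Mortality in congenital DM1 during the neonatal period has been estimated at between 30% and 40% of patients" that deaths will probably empty cohort 2. That would need all four children to have congenital DM1 and to enrol at birth. The cohort runs to 6 months and admits non-dystrophic myotonia, and entry requires clinical symptoms of myotonia. Death is also a serious adverse event, not a listed withdrawal criterion.
- A reader might infer that replaced children vanish from the tables and inflate a success rate by a known amount. The protocol defines no success endpoint and has no rule removing such children from tables.

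**Conclusion.** The point holds in limited form. The protocol permits exit from the study for outcome-related reasons, and section 3.3.3 calls for replacement of those children. Together with the ITT condition and the absence of imputation, this can bias later efficacy summaries towards children who do well. It can leave adverse events that start after withdrawal unrecorded, and it does not fit the two-year requirement for each participant. The two replacement rules contradict each other.

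The extent of bias cannot be stated. The drop from 60% to between 55% and 43% assumes that 1 to 4 children are replaced, that none of them responded, and that results are read from retained children. Whether a withdrawn child counts towards the 10 cannot be settled while evaluable is undefined. The safety results as a whole are not confined to children who stay, since treated children and their events up to withdrawal are kept. The clinical criteria for stopping treatment are not judged here.

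**What to change.** 1. In section 3.3.3, separate stopping mexiletine from ending registry data collection. Continue routine chart extraction to the end-of-treatment visit for every enrolled child, unless consent is withdrawn or the child is lost to follow-up.
2. In section 8.12, define the efficacy set as all children with at least one dose after consent, and show how many have data at each time point. This creates no missing values but keeps the denominator honest.
3. State that replacements are additional enrolments and that withdrawn children stay in all analyses and listings. Define evaluable, and say whether a withdrawn child can meet it.
4. Reconcile sections 3.3.3 and 4.1.4 on replacement, and say in section 4.1.4 whether discontinuation means the drug or the study.

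The non-imputation rule can stand, and exits need not be scored as poor outcomes. The cost is protocol wording, a few more eCRF entries for children who stop, and possibly less favourable figures.
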